3.2. Duration and Study Completion Definition

Eligible subjects after screening will collect 6 weeks of prospective baseline seizure data. Subjects will then be randomized into a 17-week, double-blind treatment phase. Participants

who complete the study or discontinue investigational product treatment before the end of the study will undergo a 2-week taper period, unless otherwise medically indicated, after which he/she will return to the site 2 weeks post last dose for a safety follow up visit. Subjects who discontinue investigational product treatment before the completion of the double-blind phase will continue to be followed per protocol and at minimum maintain daily seizure eDiary entry until the double-blind phase is completed. These subjects will also return to the site 2 weeks after the taper for safety follow-up assessments.

It is estimated that the maximum duration of subject participation in the double-blind phase will be 23 weeks, including the 17-week double-blind treatment phase and 6-week prospective baseline period, and approximately an additional 3 years for the long-term open label phase. The open-label phase will continue until the sponsor terminates the program or GNX has been approved and marketed the investigational product in the subjects' respective country.

3.3. Sites and Regions

This multicenter study is to be conducted globally, with up to 50 sites planned to participate.

3.4. Discussion of Study Design, Including the Choice of Control Group

Dosing will be based on doses that have been shown to be safe in children and adults in multiple studies with normal volunteers and individuals with epilepsy. In this current study, subjects will be randomized (1:1 ratio) to receive either GNX or PBO, prescribed in increments of 15 mg/kg/day up to 63 mg/kg/day (maximum 1800 mg/day), as an oral suspension for up to 17-weeks. The double-blind phase will be followed by an open-label phase in which all subjects will receive GNX up to an additional 3 years or more, providing long-term safety and tolerability data on GNX. Administration of GNX adjunctive therapy to background AEDs provides standard-of-care therapy in addition to any benefit that investigational product might provide.

Subjects will be randomized to receive either GNX or PBO, prescribed in increments of 15 mg/kg/day up to 63 mg/kg/day (maximum 1800 mg/day) as an oral suspension.

- 6 mg/kg three times daily (TID) (18 mg/kg/day) suspension -Days 1-7
- 11 mg/kg TID (33 mg/kg/day) suspension -Days 8-14
- 16 mg/kg TID (48 mg/kg/day) suspension - Days 15-21
- 21 mg/kg TID (63 mg/kg/day) suspension - Days 22-28

Any subject not tolerating the next dose step can be maintained at the lower dose step for additional days before advancing to next dose. If the next dose is still not tolerated, they can drop back to the next lower dose step. A minimum dose of 33 mg/kg/day and 900 mg/day must be maintained. Dose changes including alternative dosing paradigm (e.g., lower dose during the daytime and higher dose in the evening) should be discussed with the sponsor medical monitor prior to making the change or within 48 hours of making the change. The higher dose in the evening is expected to be better tolerated due to the proximity to bedtime. However, tolerability management and the final decision to adjust drug dosages lies with the Principal Investigator. Any subject who is unable to be maintained at the minimum dose should contact the sponsor to discuss continued investigational product dosing. Subjects who discontinue investigational

product should undergo a 2-week taper period unless otherwise medically indicated. Subjects who discontinue investigational product treatment before the completion of the double-blind phase will continue to be followed per protocol and at minimum maintain daily seizure diary entry until the double-blind phase is completed. These subjects should also return to the site after the taper for safety follow-up assessments.

4. STUDY POPULATION

Each subject's parent/LAR must participate in the informed consent process and provide written informed consent (and/or subject assent) before any procedures specified in the protocol are performed.

4.1. Inclusion Criteria

The subject will not be considered eligible for the study without meeting all the criteria below.

1. (a) Molecular confirmation of a pathogenic or likely pathogenic CDKL5 variant, early onset, difficult to control seizures, and neurodevelopmental impairment are required. The principal investigator (PI) must review the results of the genetic analysis and confirm that gene mutation is likely to be the cause of the epilepsy syndrome. If the patient has a *de novo* variant of unknown significance (VUS) in the kinase domain of the CDKL5, parental testing is negative and meets all other inclusion criteria, then the subject can be included. Genetic mutations will be confirmed by the sponsor's chosen central laboratory. In France, genetic mutations may be confirmed by an approved French organization, in compliance with French legislation prior to Screening Visit 1. Patients must have (b) seizure onset by 1 year of age and (c) lack of independent ambulation by 2 years of age.
2. Male or female patients aged 2 through 21 years, inclusive.
3. Subject/parent or LAR willing to give written informed consent/assent, after being properly informed of the nature and risks of the study and prior to engaging in any study-related procedures.
4. Failure to control seizures despite appropriate trial of 2 or more anti-seizure medications at therapeutic doses
5. Have at least 16 seizures of primary seizure types: bilateral tonic (sustained motor activity ≥ 3 seconds), generalized tonic-clonic, bilateral clonic, atonic/drop or focal to bilateral tonic-clonic per 28 days in each 1-month period in the 2-month period prior to screening.
6. Subject must be approved to participate by sponsor and/or designee (i.e., Epilepsy Consortium) after review of medical history, genetic testing, seizure classification, and historical seizure calendars.
7. Participants should be on a stable regimen of 0-4 anti-seizure medications (including moderate or strong inducer or inhibitor anti-seizure medications e.g. carbamazepine, phenytoin, etc.) for ≥ 1 month prior to the screening visit, without a foreseeable change in dosing for the duration of the double-blind phase. Vagus nerve stimulator (VNS), ketogenic diet, and modified Atkins diet do not count towards this limit but must be unchanged for 3 months prior to screening.
8. Subjects with surgically implanted VNS will be allowed to enter the study provided that all of the following conditions are met:
 - a. The VNS has been in place for ≥ 1 year prior to the screening visit.

- b. The settings must have remained constant for 3 months prior to the screening visit and remain constant throughout the double-blind phase.
 - c. The battery is expected to last for the duration of the double-blind phase.
9. Felbamate: The use of felbamate is allowed provided that the subject has been maintained on a stable dose of felbamate for > 6 months and has had stable liver function (aspartate aminotransferase [AST] and alanine aminotransferase [ALT]) and hematology during the course of treatment, and is expected to remain constant throughout the double-blind phase.
 10. Parent/caregiver is able and willing to maintain an accurate and complete daily electronic seizure calendar for the duration of the study.
 11. Able and willing to take investigational product with food 3 times daily. Ganaxolone must be administered with food.
 12. Sexually active female of childbearing potential must be using a medically acceptable method of birth control and have a negative quantitative serum β -human chorionic growth hormone (β -HCG) test collected at the initial screening visit. Childbearing potential is defined as a female who is biologically capable of becoming pregnant. A medically acceptable method of birth control includes intrauterine devices in place for at least 3 months prior to screening, surgical sterilization, or adequate barrier methods (e.g., diaphragm and foam). An oral contraceptive alone is not considered adequate for the purpose of this study. Hormonal oral contraceptives must also be used when a condom is used. In subjects who are not sexually active, abstinence is an acceptable form.

4.2. Exclusion Criteria

1. Previous exposure to GNX.
2. Pregnant or breastfeeding.
3. West Syndrome with hypsarrhythmia pattern on EEG or seizures predominantly of Infantile Spasm (IS) type; if EEG pattern/seizure type is uncertain, study inclusion should be reviewed and determined by the sponsor/sponsor delegate.
4. Concurrent use of adrenocorticotrophic hormone (ACTH), prednisone or other glucocorticoid is not permitted, nor use of moderate or strong inducers or inhibitors of CYP3A4/5/7. A list of CYP3A4/5/7 inhibitors and inducers is included in [Section 12.1](#). Moderate or strong inducer or inhibitor anti-epileptic drugs will be allowed (e.g., carbamazepine, phenytoin, etc.)
5. Patients on ACTH, prednisone or other systemically (non-inhaled) administered steroids should be off the product greater than 28 days prior to screening. Concomitant PRN topical or intranasal steroids for dermatologic reactions and allergic rhinitis are allowed and do not warrant exclusion from the study.
6. Subjects with a positive result on tetrahydrocannabinol (THC) or cannabidiol (CBD) test (via urine or plasma drug screen) at the screening visit, and a positive result on THC or CBD test (via plasma) at the baseline visit without prescription for Epidiolex (may go by another name in countries outside the United States) in epilepsy will be excluded from the study. Concomitant Epidiolex (CBD) use will be allowed in the double-blind phase

provided the subject has been on a stable dose for at least 1 month prior to screening and is expected to remain on a stable dose without a foreseeable change for the duration of the double-blind phase. THC and/or CBD will be allowed in the open-label phase.

7. Use of dietary supplements or herbal preparations are not permitted if subject has been using them consistently for less than 3 months prior to screening or does not plan on remaining on stable doses for the duration of the double-blind phase. Use of St. John's Wort is not permitted (See [Section 12.1](#)).
8. Changes in Anti-Epileptic Drugs (AEDs) within the last month prior to screening. All AEDs must be stable in dose for at least 1-month prior to screening unless otherwise noted.
9. Have an active CNS infection, demyelinating disease, degenerative neurological disease, or CNS disease deemed progressive as evaluated by brain imaging (magnetic resonance imaging [MRI]).
10. Have any disease or condition (medical or surgical; other than CDKL5) at screening that might compromise the hematologic, cardiovascular, pulmonary, renal, gastrointestinal, or hepatic systems; or other conditions that might interfere with the absorption, distribution, metabolism, or excretion of the investigational product, or would place the subject at increased risk.
11. An AST (serum glutamic oxaloacetic transaminase [SGOT]) or ALT (serum glutamic pyruvic transaminase [SGPT]) greater than 3 times the upper limit of normal (ULN) at study entry. If AST or ALT increases > 3 times ULN during the study, subject should be followed with weekly laboratory repeat testing and continue in study if levels trending down. Subject will be discontinued if levels do not decline to under 3 x ULN.
12. Total bilirubin levels greater than ULN at study entry. In cases of documented, stable medical condition (i.e., Gilbert's Syndrome) resulting in levels of total bilirubin greater than ULN, the medical monitor can determine if a protocol exception can be made. If total bilirubin increases to 1.5 x ULN or more during study, the subject will be discontinued.
13. Subjects with significant renal insufficiency, estimated glomerular filtration rate (eGFR) < 30 mL/min (calculated using the Cockcroft-Gault formula, Pediatric GFR calculator or Bedside Schwartz), will be excluded from study entry or will be discontinued if the criteria is met post baseline.
14. Have been exposed to any other investigational drug within 30 days or less than 5 half-lives prior to screening.
15. Unwillingness to withhold grapefruit, Seville oranges or star fruit from diet during the entire clinical trial.
16. Unwillingness to withhold alcohol throughout the entire clinical trial.
17. Have active suicidal plan/intent or have had active suicidal thoughts in the past 6 months or a suicide attempt in the past 3 years.
18. Known sensitivity or allergy to any component in the investigational product(s), progesterone or other related steroid compounds.

19. Plasma allopregnanolone – sulfate (Allo-S) levels ≥ 6.0 ng/ml at the screening visit.

4.3. Restrictions

Subjects must abstain from the use of alcohol and from consuming grapefruit, Seville oranges and starfruit until completion of the study.

4.4. Reproductive Potential

4.4.1. Female Contraception

Sexually active women of childbearing potential should be using a medically acceptable form of birth control. Women of childbearing potential must be advised to use medically acceptable birth control throughout the study period and for 30 days after the last dose of investigational product. If hormonal contraceptives are used, they should be administered per the package insert.

Women of childbearing potential who are not currently sexually active must agree to use acceptable contraception, as defined below, if they become sexually active during the period of the study and 30 days after the last dose of investigational product.

Female subjects should be:

- Premenarchal and either Tanner stage 1 or less than 9 years or age, *or*
- Surgically sterile (having undergone one of the following surgical acts: hysterectomy, bilateral tubal ligation, bilateral oophorectomy, or bilateral salpingectomy) and at least 6 weeks' post-sterilization, *or*
- Women of childbearing potential must have a negative serum pregnancy test prior to taking the first dose of investigational product and must agree to abstain from sexual activity that could result in pregnancy or agree to use a medically acceptable method of birth control.
- Abstinence is an acceptable method of birth control only if this is in line with the preferred and usual lifestyle of the patient. Periodic abstinence (e.g., calendar, ovulation, symptothermal, post-ovulation methods) and withdrawal are not acceptable methods of contraception.
- Medically acceptable methods of birth control include:
 - a. Intrauterine device plus condoms
 - b. Double-barrier methods (e.g., condoms and diaphragm with spermicidal gel or foam)
 - c. Hormonal contraceptives (oral, patch, injectable, or vaginal ring), stabilized for at least 1 month prior to screening visit, plus condoms. Note: If a woman becomes sexually active during the study, she should use one of the other acceptable methods noted above in addition to the hormonal contraceptive until it has been stabilized for 30 days prior to screening visit. Hormonal oral contraceptives must also be used when a condom is used.

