During the open-label phase, all subjects will be treated with GNX. Subjects will receive the same GNX dose given in the 17-week double-blind phase in the open-label phase of the study. However, to maintain the study blind, GNX subjects will enter into a 4-week false titration phase by increasing PBO doses in addition to maintaining GNX. Subjects who received PBO in the 17-week double-blind phase will enter a 4-week, GNX titration period in the open-label phase of the study.			
Reference Therapy, Dose and Mode of Administration: PBO is to be administered as an oral suspension with food during the 4-week, titration period of the double-blind phase of the study as follows:			

- PBO TID -Days 1-7
- PBO TID -Days 8-14
- PBO TID - Days 15-21
- PBO TID - Days 22-28

Placebo will only be used in the open-label phase of the study during the 4-week false titration phase for those subjects who were originally randomized to GNX in the 17-week double-blind phase.

Duration of treatment: Eligible subjects will collect 6 weeks of prospective baseline seizure data. Subjects will be randomized (1:1) to a 17-week double-blind treatment phase with GNX or PBO (4 weeks titration and 13 weeks dose maintenance), followed by a long-term open-label treatment phase with GNX. Following the completion of the 17-week double-blind phase, subjects randomized to PBO will transition to GNX (using false titration), while subjects randomized to GNX will stay on 63 mg/kg/day suspension (1800 mg/day maximum), or their Maximum Tolerated Dose (MTD). Subjects will begin the 4-week blinded dose titration to 63 mg/kg/day or 1800 mg/day (or MTD) after completing the final double-blind visit. It is estimated that the maximum duration of subject participation in the double-blind phase will be 23 weeks, including the 17-week double-blind treatment phase and 6-week prospective baseline period, and approximately an additional 3 years for the long-term open-label phase. The open-label phase will continue until the sponsor terminates the development of the investigational product in CDD or GNX has been approved and marketed in the subjects' respective country.

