4.4.2. Male Contraception

Male participants must agree to take all necessary measures to avoid causing pregnancy in their sexual partners during the study and for 3 months after the last dose of investigational product. Medically acceptable contraceptives include surgical sterilization (such as a vasectomy) and a condom used with a spermicidal gel or foam. The female partner of a male subject must use hormonal oral contraceptives when the male subject uses a condom. Contraceptive measures such as Plan B™, sold for emergency use after unprotected sex, are not acceptable methods for routine use.

Male subjects should not donate sperm during the study and for 30 days after the last dose of investigational product.

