Following the completion of the 17-week, double-blind phase, subjects randomized to PBO will transition to GNX while subjects randomized to GNX will stay on 63 mg/kg/day suspension (maximum 1800 mg/day or Maximum Tolerated Dose [MTD]). Subjects will begin the 4-week blinded dose titration to 63 mg/kg/day or 1800 mg/day (or MTD) after completing Visit 5.

In order to maintain the blind of the double-blind phase, all subjects will be required to dose from 2 groups of bottles: Bottle Group A- maintenance and Bottle Group B- titration. In addition to the maintenance dose from Bottle Group A, subjects will be instructed to take a second dose from Bottle Group B. For subjects initially randomized to GNX, Bottle Group A will contain GNX while Bottle Group B will contain PBO. For subjects initially randomized to PBO, Bottle Group A will contain PBO while Bottle Group B will contain GNX.

Dosing from both Bottle Group A and Bottle Group B will begin at the end of Visit 5 (Week 17), the last visit in the double-blind phase, and continue until the end of the open-label 4-week titration period when subjects return to the site for evaluation (Visit 7, Week 21). Subjects will have an interim safety visit at Visit 6 (Week 19) 2 weeks after starting the open-label phase in which they will receive a new set of medication bottles (Table 6).

**Table 6: Transition from Double-blind to Open-label: Oral Suspension (50 mg/ml)
 Dosing for Subjects ≤ 28 kg**

Titration Day	Bottle Group A- Maintenance	Bottle Group B- Titration
	DB GNX: GNX bottle	DB GNX: Placebo bottle
	DB Placebo: Placebo bottle	DB Placebo: GNX bottle
	Bottle Group A Dose	Bottle Group B Dose
1-7	63 mg/kg/day (21 mg/kg TID)	18 mg/kg/day (6 mg/kg TID)
8-14	63 mg/kg/day (21 mg/kg TID)	33 mg/kg/day (11 mg/kg TID)
Visit 6, Week 19	Safety visit and new set of Group A and Group B bottles issued	
15-21	63 mg/kg/day (21 mg/kg TID)	48 mg/kg/day (16 mg/kg TID)
22-28	63 mg/kg/day (21 mg/kg TID)	63 mg/kg/day (21 mg/kg TID)
Visit 7, Week 21	One set of GNX bottles dispensed, return to dosing from 1 bottle at a time	
	63 mg/kg/day (21 mg/kg TID)	

DB = double-blind; GNX = ganaxolone; TID = three times daily.

An example of the transition from double-blind to open-label dosing is shown in Table 7 for a 20 kg subject who was initially randomized to GNX during the double-blind phase.

Table 7: Example of Double-blind to Open-label: DB GNX Subject Weighing 20 kg- Suspension Dosing (50 mg/ml)

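### The contraception rules conflict on IUDs and back-up, and the visit tables, at odds with Section 7.6.5, mark no pregnancy test between Visit 2 and the final open-label or taper visit

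*Protocol*

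**What the plan says.** **Methods.** Criterion 12 (synopsis and Protocol 4.1) says that an acceptable method "includes intrauterine devices in place for at least 3 months prior to screening, surgical sterilization, or adequate barrier methods". No condom is required with the IUD. Protocol 4.4.1, item a, lists "Intrauterine device plus condoms".

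**Back-up.** The note under 4.4.1, item c, concerns a woman who becomes sexually active during the study. She is to add another method to her hormonal one "until it has been stabilized for 30 days prior to screening visit".

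**Condoms.** Section 4.4.1 (under item c) and criterion 12 both state: "Hormonal oral contraceptives must also be used when a condom is used". Section 4.4.2 has a parallel rule for partners of male subjects: "The female partner of a male subject must use hormonal oral contraceptives when the male subject uses a condom".

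**Testing.** Section 4.4.1 requires: "Women of childbearing potential must have a negative serum pregnancy test prior to taking the first dose of investigational product". Table 1 marks the pregnancy test at Visits 1 and 2 only. Table 2 marks it at the final open-label/taper visit and the post-taper safety follow-up only. The visit lists in 7.2 agree with the tables, and so do the copies in the SAP. Section 7.6.5, however, says that laboratory assessments are collected at every clinic visit and names the serum pregnancy test among them. Appendix 12.2 lists serum beta-HCG.

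**Treatment.** After Visit 5, "subjects randomized to PBO will transition to GNX" (6.2.3). The synopsis expects "approximately an additional 3 years for the long-term open-label phase".

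**The concern.** A site that reads criterion 12 and then 4.4.1 cannot tell whether an IUD user also needs condoms. A site that applies the back-up note to a newly started hormonal method has no date on which back-up may stop.

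The testing schedule matters more. Under the tables, a placebo subject has her first exposure to ganaxolone without a fresh test. A girl who reaches childbearing potential after Visit 2 has no scheduled test while she stays on open-label treatment, although 7.6.6 has her Tanner stage assessed annually. Section 8.1.6 requires a pregnant participant to be withdrawn. Without a scheduled test, detection depends on adverse-event review, examinations or an unscheduled test. The condition affects mainly girls (2.1), and the eligible ages of 2 to 21 years span puberty.

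**Working it through.** **Wording, side by side**

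| Topic | Criterion 12 | Section 4.4.1 | Result |
|---|---|---|---|
| IUD | Alone, in place at least 3 months | With condoms | Direct conflict |
| Patch, injectable, ring | Not listed | With condoms | Lists differ; both are introduced by a form of *include*, so neither is stated to be exhaustive |
| Oral contraceptive with condom | Tied to no method | At the end of item c | Scope unclear |

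The back-up note has two cases:

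- The hormonal method was already stable for 30 days at screening. The end condition is met at once and the note does not bind.
- The method was started or changed after that point. Screening is already past when the woman becomes sexually active on study, so the condition cannot be reached.

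**Testing interval**

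Inputs: Visit 2 is Week 0. Visit 5 is Week 17. Open-label ganaxolone starts after Visit 5. The open-label phase lasts about 3 years (synopsis and 3.2). After Week 68, clinic visits come every 16 weeks (7.2.6.3).

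The plan's own duration figure reproduces: 6 + 17 = 23 weeks.

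Placebo subjects, last test to first ganaxolone: 17 − 0 = 17 weeks, or 17 × 7 = 119 days.

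Visit 2 to the final open-label visit is 17 + 52 × (open-label years):

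| Open-label years | Weeks without a scheduled test |
|---|---|
| 1 | 17 + 52 = 69 |
| 2 | 17 + 104 = 121 |
| 3 | 17 + 156 = 173 |
| 4 | 17 + 208 = 225 |

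In the 3-year case, 14 clinic visits fall inside the gap with no test marked: Weeks 5, 9, 17, 19, 21, 34, 52, 68, 84, 100, 116, 132, 148 and 164.

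**What added tests would achieve (3-year case)**

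| Tests added at weeks | Assays | Successive gaps (weeks) | Longest |
|---|---|---|---|
| 17, 52, 100, 148 | 4 | 17, 35, 48, 48, 25 | 48 |
| 17, 34, 52, 68, then every 16 weeks to 164 | 10 | 17, 17, 18, 16 (seven times), 9 | 18 |
| All 14 intermediate clinic visits | 14 | – | 18 |

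The 18-week gap can reach 20 weeks if the Week 34 visit is 7 days early and the Week 52 visit 7 days late. Testing at all 14 visits does not shorten the longest gap any further.

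**The case against.** **Section 7.6.5 already provides for testing.** This is the strongest reply. Read with Appendix 12.2, that section can put the test in the panel at every clinic visit, so it goes too far to say that the protocol simply has no test in the interval. But 7.6.5 also sends the reader to Tables 1 and 2 for timing. There the pregnancy test has its own row, and the laboratory-row footnote covers only chemistry and hematology. The tables are the stronger reading. What stands is a conflict that sites would have to resolve for themselves.

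**A cautious site can satisfy both IUD rules.** An IUD in place for 3 months plus condoms meets both lists. This holds only if the oral-contraceptive sentence is confined to item c. Read generally, as its unattached position in criterion 12 allows, it would add a pill to the IUD and condoms.

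**The back-up note errs on the safe side.** True: where its end cannot be reached, back-up simply continues. The wording is still wrong.

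**Practical exposure is small.** Entry requires lack of independent ambulation by age 2, Section 10.3.1 says that subjects cannot consent for themselves, and abstinence is accepted. This stands, and it limits the weight of the point.

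**Double-blind discontinuers may be covered.** Section 7.2.3, which names the taper and early-termination visit, omits the test. A reader might infer a wait of up to 17 + 2 + 2 = 21 weeks, to the post-taper safety visit. The documents do not establish that. Table 2's taper column is also headed for early discontinuation and marks the test; 7.2.7 covers early termination; and SAP 1.2.5 and 7.1.1 suggest that these subjects have a taper visit. The text is ambiguous, so it needs clarifying.

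**Conclusion.** The point holds as a set of conflicting instructions plus a long interval with no test marked in the tables. If sites follow the tables, the interval is about 17 weeks before a placebo subject's first ganaxolone dose. For a subject who stays open-label it is about 173 weeks, assuming 3 years of 52 weeks (69 to 225 weeks for 1 to 4 years). An open-label discontinuer has a shorter interval, because the 7.2.7 taper visit includes the test.

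Three stronger readings are not supported:

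- That the back-up rule can never be met. It fails only for a hormonal method not already stable for 30 days at screening.
- That starting placebo subjects on ganaxolone untested breaches 4.4.1. The rule concerns the first dose of investigational product, Section 6.1 includes placebo under that heading, and the Visit 2 test therefore satisfies it. A test at Visit 5 would be a sensible addition.
- That the documents fix a minimum open-label testing frequency. They do not; it is a judgement for the sponsor.

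This is a low-cost participant-safety improvement. The documents give no pregnancy rate and no sexual-activity rate, so the expectation of few events is an assumption from the severity of the disorder. Type I error, power and the efficacy analyses are unaffected.

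**What to change.** 1. Use one list of methods in the synopsis, 4.1 and 4.4.1, and state whether an IUD needs condoms.
2. End the 4.4.1 back-up note with *until used stably for 30 days*.
3. Delete the oral-contraceptive sentence or limit it to condom-only use in the synopsis, 4.1 and 4.4.1, and align 4.4.2.
4. Add serum beta-HCG for subjects of childbearing potential, including those who reach it on study. Test at Visit 5, before open-label ganaxolone, and then periodically at open-label visits that already draw blood. Frequency is the sponsor's choice; pairing it with annual Tanner staging is one option.
5. State that the taper-visit test applies to subjects who discontinue in the double-blind phase.
6. Align Tables 1 and 2, Sections 7.2.3, 7.2.6.2, 7.2.6.3 and 7.6.5, Appendix 12.2 and the SAP copies of the tables.

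Cost: wording changes, no extra visit, and over a 3-year open-label phase 4 assays (about yearly) to 10 assays (every main clinic visit from Visit 5) per subject of childbearing potential. This assumes that the assay can share the existing draw. The documents give no sample volumes, so slightly more blood may be needed. Premenarchal girls at Tanner stage 1 or under 9 years form a separate group in 4.4.1 and would not be tested.
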